8.4.5 Adverse Events Based On Signs and Symptoms

All AEs spontaneously reported by the patient or reported in response to the open question from the study personnel: “Have you had any health problems since you were last asked?” or revealed by observation will be collected and recorded in the CRF. When collecting AEs, the recording of diagnoses is preferred (when possible) rather than recording a list of signs and symptoms, for example: congestive heart failure rather than low ejection fraction, rales and dyspnea. However, if a diagnosis is known and there are other signs or symptoms that are not generally part of the diagnosis, the diagnosis and each sign or symptom not part of the diagnosis will be recorded separately, for example: congestive heart failure and conjunctivitis.

8.4.6 Adverse Events Based On Examinations and Tests

Deterioration as compared to baseline in protocol-mandated laboratory values, vital signs and other safety variables will only be reported as AEs if they fulfil any of the SAE criteria or are the reason for discontinuation of treatment with the investigational product. If deterioration in a laboratory value/vital sign is associated with clinical signs and symptoms, the sign/symptom will be reported as an AE and the associated laboratory result/vital sign will be considered as additional information. Any new or aggravated clinically relevant abnormal medical finding at a physical examination as compared with the baseline assessment will be reported as an AE.

Clinically relevant deterioration in non-protocol-mandated measurements will be reported as AE(s). Wherever possible the reporting investigator uses the clinical, rather than the laboratory term (e.g., anaemia *versus* low haemoglobin value).

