8.1.4 Adverse Events

AEs will be recorded during the trial period, from obtaining the informed consent to the follow-up visit. For further information on definitions and reporting of AEs and SAEs, see Section 8.4.

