8.1.5 Clinical Laboratory Variables

8.1.5.1 Clinical Chemistry and Haematology

Blood samples for safety laboratory evaluations of clinical chemistry and haematology parameters (see Table 3) will be collected at the time-points indicated in the study flow chart. Actual sampling time will be recorded. Clinically significant abnormal findings will be reported as AEs. The clinical chemistry and haematology will be analysed locally.

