8.1.6 Electrocardiogram

The 12-lead ECG will be recorded with a validated ECG device. The parameters for heart rate (HR), PR interval, RR, QRS, QT and QTc(F) will be assessed (i.e., QT correction according to the Fridericia formula $QTcF=QT/RR^{0.33}$). ECG recordings will capture at least

four QRS complexes, i.e., evaluable RR intervals. The Investigator or designee will evaluate whether the ECG is normal or abnormal and whether it is clinically significant, if abnormal. Any occurrence or de- or re-polarization disorders, arrhythmic disorders or other abnormalities will be assessed and any changes compared to the baseline (i.e., predose, treatment day 0) record will be commented. Clinically significant abnormal findings will be reported as AEs.

Additional ECGs may be collected by the Investigator for safety reasons.

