8.4.1 Definition of Adverse Events

An adverse event (AE) is the development of an undesirable medical condition or the deterioration of a pre-existing medical condition following or during exposure to a pharmaceutical product, whether or not considered causally related to the product. Relationship to the study drug will be deemed as not related, unlikely, possible or probable. An undesirable medical condition can be symptoms (e.g., nausea and chest pain), signs (e.g., tachycardia and enlarged liver) or the abnormal results of an investigation (e.g., laboratory findings and electrocardiograms).

In cases of surgical or diagnostic procedures, the condition/illness leading to such a procedure is considered as the AE rather than the procedure itself.

In case of a fatality, the cause of death is considered as the AE, and the death is considered as its outcome.

Pre-treatment Adverse Event

A pre-treatment adverse event is any untoward medical occurrence arising or observed between signing of informed consent and the first administration of the IMP.

Treatment Emergent Adverse Event

A treatment emergent adverse event is any AE occurring after the administration of the IMP and within the time of residual drug effect, or a pre-treatment adverse event or pre-existing medical condition that worsens in intensity after administration of the IMP and within the time of residual drug effect.

The time of residual drug effect is the estimated period of time after the administration of IMP, where the effect of the product is still considered to be present based on PK, PD or other substance characteristics. The residual drug effect is generally accepted to be 5 times the terminal half-life. Based on the data from healthy subjects, the terminal half-life of IdeS is expected to be approximately 5 days (mean of 118 hours in healthy subjects), i.e., in this study the residual drug effect is likely to be well within the 30 day visit.

Post-treatment Emergent Adverse Events

A post-treatment emergent adverse event is any event occurring after the time of residual drug effect of the IMP, i.e., from the visit on day 30.

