8.4.2 Definition of Serious Adverse Events

A serious adverse event (SAE) is an AE or suspected adverse reaction (SAR) that is considered "serious" if, in the view of either the investigator or sponsor, it results in any of the following outcomes:

- Results in death
- Is immediately life-threatening
- Requires in-patient hospitalisation or prolongation of existing hospitalisation.
- Results in persistent or significant disability or incapacity
- Is a congenital abnormality or birth defect
- Is an important medical event that may jeopardise the patient or may require medical intervention to prevent one of the outcomes listed above

Important medical events that may not result in death, be life-threatening, or require hospitalization may be considered as SAEs when, based upon appropriate medical judgment, they may jeopardize the subject or may require medical or surgical intervention to prevent one of the outcomes listed in this definition. Examples of such events include allergic bronchospasm requiring intensive treatment in an emergency room or at home, blood dyscrasias or convulsions that do not result in inpatient hospitalization, or the development of drug dependency or drug abuse.

Life-threatening event: An adverse event or suspected adverse reaction is considered "life-threatening" if, in the view of either the investigator or sponsor, its occurrence places the patient or subject at immediate risk of death. It does not include an adverse event or suspected adverse reaction that, had it occurred in a more severe form, might have caused death.

Disability is defined as a substantial disruption in a person's ability to conduct normal life functions.

Hospitalization for inpatient hospitalization or prolongation of existing hospitalization.

- In this study for elective treatment of a pre-existing condition that did not worsen during the clinical investigation is not considered an AE. Hospitalisation for study drug dosing and observation as required by protocol is not considered an SAE. Admittance to an emergency room for observation without being admitted to the hospital may be considered to be an AE but is not considered as an SAE. However, complications that occur during hospitalization are AEs, and if a complication prolongs hospitalization, the event is considered serious.

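### Protocol 8.4.6 contradicts 8.1.3, 8.1.5.1 and 8.1.6 on when an abnormal result at a scheduled test is reported as an adverse event

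*Protocol*

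**What the plan says.** Three assessment sections of the protocol carry one unconditional sentence: "Clinically significant abnormal findings will be reported as AEs". It appears in 8.1.3 for vital signs, in 8.1.5.1 for clinical chemistry and haematology, and in 8.1.6 for ECGs.

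Protocol 8.4.6 covers worsening from baseline in protocol-mandated laboratory values, vital signs and other safety variables. These will "only be reported as AEs if they fulfil any of the SAE criteria or are the reason for discontinuation of treatment", meaning treatment with study drug. Where symptoms accompany the change, "the sign/symptom will be reported as an AE" and the measured value is supporting information.

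Three other sections bear on the question:
- Protocol 8.4.1 defines AEs broadly enough to include abnormal laboratory and ECG results, with no condition on seriousness or stopping treatment.
- Protocol 8.4.2 lets judgement make an event serious, through the criterion "Is an important medical event that may jeopardise the patient".
- Protocol 8.1.4 links the two sets of rules with a cross-reference: "For further information on definitions and reporting of AEs and SAEs, see Section 8.4".

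The SAP gives no AE reporting rule.

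**The concern.** An investigator who finds a clinically significant but silent and non-serious change at a scheduled test has two instructions that cannot both be followed. An example is a raised creatine kinase without muscle symptoms. Protocol 3.7 says creatine kinase will be assessed, directly after discussing earlier reports of myalgia.

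The choice has consequences because several parts of the plan work only on AEs. Severity grade and causality are recorded for each AE (8.4.4). The type, frequency and intensity of AEs form part of the primary endpoint (4.2.1). A dose-limiting toxicity is a novel AE of grade 3 or more with a possible relationship to the drug (5.4), and one such event at 0.25 mg/kg rules out escalation (5.3). The committee must be convened when two or more patients have a related grade 3 event (5.5). A change never entered as an AE has no required grade or causality rating on which these rules could act.

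**Working it through.** No figure in the plan is at issue, so the check sets the rules side by side and looks for a statement of precedence.

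**1. Does 8.4.6 cover the same measurements?** It names laboratory values and vital signs. It does not name ECG, but Protocol 14.2.2 lists ECG among the safety variables, so the phrase about other safety variables reasonably includes it. The conflict for laboratory values and vital signs does not depend on that reading. In the other direction, 8.1.5.1 names only chemistry and haematology. Urinalysis (8.1.5.2) has no sentence on clinical significance, and coagulation has its own heading in Table 3 and is not named in 8.1.5.1. The conflict is therefore shown for chemistry, haematology, vital signs and ECG, and not for urinalysis or coagulation.

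**2. Where do the rules diverge?**

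| Finding at a scheduled post-dose test | 8.1.3, 8.1.5.1, 8.1.6 | 8.4.6 | Conflict |
|---|---|---|---|
| Clinically significant and meets an SAE criterion | AE | AE | No |
| Clinically significant and the reason for stopping treatment | AE | AE | No |
| Clinically significant, non-serious, with symptoms | AE | Symptom is the AE, value is supporting information | Small: an AE is entered either way |
| Abnormal but unchanged from baseline | AE if clinically significant | Not a deterioration, so not restricted | No |
| New, clinically significant, asymptomatic, non-serious, treatment not stopped | AE | Not an AE | Yes |

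Only the last row is a direct contradiction.

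**3. Does the discontinuation exception close the gap?** Treatment is one 30-minute infusion (7.1.5). Sampling times on day 0 run from the start of infusion (7.2). By Table 2, the first post-dose laboratory sample is at 2 h and the first vital signs and ECG are at 6 h.
- Laboratory: 120 − 30 = 90 min, or 1.5 h after the planned end of infusion.
- Vital signs and ECG: 360 − 30 = 330 min, or 5.5 h after the planned end.

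If the exception means stopping the infusion, it would not normally apply at any scheduled post-dose test. If it also covers leaving the study, it could apply later, but the last row of the table is unaffected because nothing is stopped there.

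**4. Is there an order of precedence?** The cross-reference in 8.1.4 offers further information and does not say that 8.4 overrides 8.1. Section 8.4 is not uniform either, since the definition in 8.4.1 includes abnormal investigation results that 8.4.6 would leave unreported. No other text available for review settles it.

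**The case against.** The strongest reply accepts the conflict in wording and argues that little follows from it. Most of that stands.

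- **The data are not lost.** The SAP lists safety laboratory values, ECGs and vital signs (4.2), plots repeated measurements and marks out-of-range values where ranges exist (4.3). Chemistry, haematology and coagulation go directly into the escalation evaluation (Protocol 5.1, 5.3), and the committee assesses each patient (5.5). This stands. What is missing is the classification, grade and attribution.
- **A DLT is defined by an AE, not by a reported AE.** Protocol 8.4.6 limits reporting and does not redefine an AE, so a related grade 3 value could still be recognised as a DLT from the laboratory data. This stands too. The weakness is only that such a value might not arrive through AE reporting.
- **The SAP plans no AE tabulation.** SAP 4.1 and 5 drop the summaries, and none of the ten listings named in 4.2 is an AE listing, although 4.1 says all data will be listed. So a distorted AE count in a planned table cannot be claimed. The two patients' AE records still depend on the rule that was used.
- **Documents not seen may settle it.** The CRF instructions (Protocol 7.3.1), the Data Management Plan (12.4) and the report were not available. This is possible, and it would make the fix simpler without removing the contradiction in the protocol.

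A reader might also infer that 8.4.6 treats the same ECG change differently on an unscheduled recording, because it reports clinically relevant deterioration in non-mandated measurements and 8.1.6 says: "Additional ECGs may be collected by the Investigator for safety reasons". That depends on reading non-mandated as extra repeats of a required test. It can equally mean types of test that the protocol does not require, in which case the difference disappears. The point is not relied on.

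**Conclusion.** The contradiction is real and the protocol is wrong as written. For one class of finding (new, asymptomatic, clinically significant, non-serious, at a scheduled test, treatment not stopped), 8.1.3, 8.1.5.1 and 8.1.6 require an AE and 8.4.6 excludes one. The conclusion rests on the plain wording, on counting ECG as a safety variable as 14.2.2 does, and on no unseen text setting precedence.

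The consequence is bounded. Such a change could be missing from the AE part of the primary endpoint and lack a grade and causality rating. It concerns two treated patients whose underlying measurements remain visible.

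Two stronger conclusions are not supported. A reader might infer that a dose-escalation decision is still at risk. It is not: the SAP (section 1 and 2.1) records that the trial stopped after two patients, and the review in Protocol 5.3 was due after three. A reader might also count the scheduled post-dose tests in Table 2 as a measure of the effect. Those are occasions for testing, and the documents give no rate at which the conflicting class arises, so no probability or number of missed AEs can be derived.

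**What to change.** If the protocol text is reused, reconcile the first sentence of 8.4.6 with 8.1.3, 8.1.5.1, 8.1.6 and 8.4.1. A single AE reporting rule should then apply to scheduled tests and feed CTCAE grading, causality rating, DLT assessment and the trigger in 5.5. The documents do not show which rule was intended, so the sponsor must decide.

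For the closed trial:
1. State in the report, in one sentence, which rule was applied to the two treated patients' AE records.
2. Check their safety laboratory, vital-sign and ECG listings for clinically significant changes not recorded as AEs, and report what is found.

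The cost is a sentence in the report and a check of two patients' listings, plus a wording change on reuse. The downside is possibly a few more AE entries.

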8.4.7 Follow-up of Unresolved Adverse Events

Any AEs that are unresolved at the patient’s last AE assessment in the study are followed up by the investigator until stabilization, for as long as medically indicated or the overall clinical outcome of the patient is known, unless the patient is documented as “lost to follow-up”. All SAEs and AEs leading to discontinuation should be followed until the event resolves, stabilizes, or returns to baseline.

Reasonable attempts to obtain this information must be made and documented. Sponsor retains the right to request additional information for any patient with ongoing AE(s)/SAE(s) at the end of the study, if judged necessary.

8.4.8 Reporting of Serious Adverse Events

All SAEs have to be reported, whether or not considered causally related to the investigational product, or to the study procedure(s). All SAEs will be recorded in the CRF. SAEs will be recorded from the time of informed consent.

All SAEs must be reported, whether or not considered related to the study drug, on a separate SAE Report Form. All SAEs will also be recorded in the CRF. An assigned contract research organisation ([REDACTED]) will be responsible for reporting all SAEs to regulatory authorities and ethics committees in accordance with International conference on harmonisation (ICH) Good Clinical Practice and local regulations. As soon as the Investigator is aware of a potential SAE he/she should contact [REDACTED] by fax or e-mail and in any case *no later than 24 hours* after the knowledge of such a case. At the time of initial reporting the investigator must provide as a minimum requirement, patient number, birth date, description of the SAE and a preliminary assessment of causality.

[REDACTED]	[REDACTED]
[REDACTED]	[REDACTED]
[REDACTED]	[REDACTED]
[REDACTED]	[REDACTED]
[REDACTED]	[REDACTED]

For fatal or life-threatening adverse events where important or relevant information is missing, active follow-up is undertaken immediately. Investigators or other site personnel inform the sponsor and monitor of any follow-up information on a previously reported SAE immediately but no later than within 24 hours of when he or she becomes aware of it. The monitor or sponsor will advise the investigator/study site personnel how to proceed.

The SAE reporting procedures are detailed in the study specific Safety Management Plan. This plan is an agreement between the sponsor, and [REDACTED].

8.4.9 Reporting of Suspected Unexpected Serious Adverse Reactions (SUSARs)

Suspected unexpected serious adverse reactions (SUSARs) must be reported to Regulatory Authorities. A suspected serious adverse reaction is any serious adverse event for which there is a reasonable possibility that the investigational product caused the adverse event. A serious adverse reaction is considered "unexpected" if it is not listed in the Reference Safety Information section of the investigator brochure or is not listed at the specificity or severity that has been observed.

SUSARs with an outcome of death or are life threatening must be reported to the relevant Regulatory Authorities within 7 calendar days, all other SUSARs must be submitted within

15 calendar days. The SUSAR reporting procedures are detailed in the study Safety Management Plan. This plan is an agreement between the sponsor, and [REDACTED]. The sponsor will notify the appropriate regulatory agency(ies) and all participating site Investigators of any SUSARs on an expedited basis and in accordance with applicable regulations. In addition, the sponsor is responsible for informing all investigators in all ongoing studies involving IdeS about all SUSARs.

It is the responsibility of the site Investigator to promptly notify the Ethics Committee and other appropriate institutional regulatory bodies of all SUSARs received involving risk to human subjects as per their applicable requirements.

9. BIOLOGICAL SAMPLING PROCEDURES

9.1 Volume of Blood

The maximum volume to be drawn from each patient in the study will not exceed 300 mL.

9.2 Handling, Storage and Destruction of Biological Samples

Safety samples will be used or disposed after analyses.

9.2.1 Pharmacokinetic, Pharmacodynamic and Anti-drug Antibody Samples

Samples will be shipped to [REDACTED] for analysis either in house or at external laboratory. Study samples may be stored for a maximum of two years after completion of the study report.

9.3 Chain of Custody of Biological Samples

A full chain of custody is maintained for all samples throughout their life cycle.

The principal investigator keeps full traceability of collected biological samples from the patients while in storage at the centre until shipment and keeps documentation of receipt of arrival.

The sample receiver keeps full traceability of the samples while in storage and during use until used or disposed.

Sponsor keeps oversight of the entire life cycle through internal procedures, monitoring of study sites and auditing of external laboratory providers.

9.4 Withdrawal of Informed Consent for Donated Biological Samples

If a patient withdraws consent to the use of biological samples donated the samples will be disposed/destroyed, if not already analysed and documented.

The principal investigator:

- will ensure that patient withdrawal of informed consent is notified immediately to sponsor
- will ensure that biological samples from that patient, if stored at the study site, are immediately identified, disposed/destroyed and the action documented.
- will ensure the laboratory(ies) holding the samples is/are informed about the withdrawn consent immediately and that samples are disposed/destroyed and the action documented returned to the study site.

Sponsor ensures the laboratory(ies) holding the samples is/are informed about the withdrawn consent immediately and that samples are disposed/destroyed and the action documented returned to the study site.

In the event that analysis/research has already been performed, sponsor will retain the results and associated data for regulatory reasons but these will not be used in any subsequent analyses.

10. ETHICAL AND REGULATORY REQUIREMENTS

10.1 Ethical Conduct of the Study

The study will be performed in accordance with ethical principles that have their origin in the Declaration of Helsinki and are consistent with ICH/Good Clinical Practice, applicable regulatory requirements.

10.2 Patient Data Protection

The informed consent form (ICF) will incorporate wording that complies with relevant data protection and privacy legislation.

10.3 Ethics and Regulatory Review

An ethical review board must approve the final study protocol, including the final version of the ICF and any other written information to be provided to the patients. The investigator will ensure the distribution of these documents to the applicable ethical review board, and to the study site staff. The opinion of the ethical review board must be given in writing.

Sponsor must approve any modifications to the ICF that are needed to meet local requirements.

Before enrolment of any patient into the study, the final study protocol, and the final version of the informed consent form are approved by the national regulatory authority or a notification to the national regulatory authority is done, according to local regulations.

The distribution of any of these documents to the national regulatory authorities will be handled by sponsor.

Sponsor will provide ethical review boards and principal investigators with safety updates/reports according to local requirements.

Progress reports and notifications of serious and unexpected adverse drug reactions will be provided to the ethical review board according to local regulations and guidelines.

